The potential therapeutic benefits of increased FGF19 pathway activity in metabolic disease and NASH is well documented in various animal models of disease. For example, aldafermin has been evaluated in various mouse animal models of NASH, and has demonstrated improvement in the histologic, biochemical, and fibrogenic biomarkers associated with NASH-related hepatic injury (Study 13-PD-NGM282-1007). Furthermore, aldafermin produced significant reduction in steatosis, inflammation, and ballooning in mouse models of NASH (Zhou 2017). Importantly, aldafermin is devoid of proliferative activity based on chronic evaluation in rodents and non-human primates that is a potential limitation of FGF19 as a therapeutic agent (Zhou 2014). Aldafermin was selected from more than 160 variants of human FGF19 that were screened to retain robust efficacy while lacking evidence of proliferative activity in db/db mice (Luo 2014, Zhou 2014, DePaoli 2019).

The safety, tolerability, pharmacokinetics (PK), and pharmacodynamics (PD) of aldafermin have been studied in a blinded, placebo-controlled, single-ascending-dose (SAD) and multiple-ascending-dose (MAD) study in normal subjects (Study 12-0101) and in subjects with T2D (Study 13-0102). Aldafermin was safe and generally well tolerated with dose-dependent mild to moderate injection-site reactions (ISRs), increases in total cholesterol and gastrointestinal (GI) symptoms (loose stools, abdominal cramping, nausea) the most common drug-related adverse events (AEs), which were observed mainly with higher doses. Dose-dependent significant reductions in serum C4 levels were also observed after administration of aldafermin in both populations supported target engagement and suppression of CYP7A1.

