2. The primary safety endpoint is frequency, severity, and timing of adverse events (AEs) and serious adverse events (SAEs). Safety and tolerability of aldafermin in subjects with NASH as a function of dose level after up to 24 weeks of treatment with aldafermin will be assessed.

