^c During screening, sites will complete; i) AUDIT-C alcohol consumption questionnaire and, ii) document subject- reported alcohol consumption to confirm whether amounts are within protocol defined limits (refer to exclusion criterion #19)

^d Screening Day -28 MRI-PDFF (includes [REDACTED]) will serve as baseline for efficacy endpoint analysis. The Screening MRI result is valid for up to 8 weeks and may be used for a subject who is re-screened within that time frame. [REDACTED]

^e All subjects are required to have a liver biopsy result at Screening and additional liver biopsy at Week 24. A Screening liver biopsy will be performed only in subjects who do not have a historical biopsy available within 6 months of Screening.

^f Adverse events will be monitored and recorded from subject signing informed consent through follow-up.

^g Serum chemistry will include ALT, AST, ALP, bicarbonate, bilirubin (direct and total), BUN, calcium, chloride, creatinine, CK, GGT, glucose, HDL, LDL, lipase, phosphate, potassium, proteins (albumin, total protein), sodium, total cholesterol, and TG. Lab results for ALT, AST, total cholesterol, LDL, HDL, and triglycerides are blinded to the site and sponsor from Week 2 onward.

^h Creatine Kinase will be collected at Day -42, Day 1 and Week 12, and Week 24.

ⁱ A serum pregnancy test will be performed on all female subjects of childbearing potential at Day -42, -28 Screening visits and Day 1 (pre-dose). A urine pregnancy test will be performed on all female subjects of childbearing potential at Weeks 4, 12, 24, and 30. If the urine pregnancy test is positive, a serum pregnancy test will be performed to confirm

results.

^j Urine drug and alcohol screens may be repeated during treatment for subjects suspected of excessive alcohol intake or to rule out association with a safety event

^k C4 and bile acid testing will be collected at Day 1 and Weeks 2, 4, 8, 12, 18, 24, 25 and 30. In addition, for subjects participating in the optional PK sub-study, additional C4 will be tested at the same timepoints as the PK blood sample collections: Day 1 and Week 24 at pre-dose, and post-dose at 0.5, 1, 2, 4, 6, 8, 12, and 24 hours.

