9.2.4 Week 2 Procedures

Subjects will report to clinic fasted and not dosed with aldafermin/matched placebo. The following procedures will be performed:

Pre-dose:

- Measure vital signs (including temperature, respiratory rate, and seated blood pressure and pulse)
- Record concomitant medications
- Record AEs
- Obtain blood for 10-hour fasted clinical laboratory samples
 - Chemistry
 - CBC
 - INR
 - Lipid panel
 - Lipoprotein particles
 - Lipase
 - C4 and serum bile acids
 - PK (pre-dose)
 - ADAs
 - NAbs

Results for ALT, AST, Total Cholesterol, LDL, HDL, and triglycerides are blinded to the site and sponsor.

In-clinic dosing and dispensing:

- Collect old aldafermin/matched placebo study-drug kit/diary and conduct reconciliation
- Dispense new aldafermin/matched placebo study-drug kit/diary
- Dispense rosuvastatin medication/diary
- Oversee subject's aldafermin/matched placebo study-drug self-administration (from new kit).
- Perform LISSA evaluation

Before clinic discharge:

- Remind subject to bring study-drug kit/diary and to not self-inject aldafermin/matched placebo on clinic visit days
- Schedule Week 4 visit

Lipid-Lowering Therapy Assessment:

The third-party Medical Monitor will evaluate LDL-C results to assess the need for lipid-lowering therapy (refer to [Section 9.4.14](#)).

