9.4.14 Lipid-Lowering Therapy Assessment

LDL-C will be evaluated at all study visits for possible increases in lipid levels associated with aldafermin administration. Rosuvastatin will be started in subjects meeting specific LDL-C level criteria at Week 2. Rosuvastatin and matched placebo are over-encapsulated in bottles of 35 capsules ([Section 10.4.2](#)). Initiation and ongoing dose adjustments of rosuvastatin will be managed by an unblinded third-party Medical Monitor and through the [REDACTED]. Lipid levels will be blinded to the sponsor and site. Initiation and dose adjustments will be determined by the lipid levels collected at Weeks 2, 4, 8, 12, and 18. LDL-C samples will be analyzed and reported to the third-party Medical Monitor. Bottles of rosuvastatin and/or matching placebo will be dispensed at each study visit through Week 18 (statin naïve) or Week 24 (statin experienced) as instructed through [REDACTED] [REDACTED] [REDACTED]. The subject will be sent home from their clinic visit with the IVRS assigned bottle(s) and instructed to refrain from dosing until told from which bottle or bottles to dose by the study site. The third-party Medical Monitor will review the LDL-C level and assign the dose of rosuvastatin [REDACTED] [REDACTED] based on the dosing algorithm ([Appendix 3](#)). The site will subsequently communicate to the subject the assigned bottle(s) and dosing should be immediately initiated.

Subjects who have not responded adequately to rosuvastatin (defined as >100 mg/dL and > 15 mg/dL above their Day1 LDL-C level), and who are currently receiving their maximum tolerated rosuvastatin dose, will be considered for additional lipid-lowering therapy (ezetimibe). The third-party Medical Monitor will contact the site regarding any subject meeting this criterion. Ezetimibe will be prescribed and taken as second-line treatment per investigator judgement and approval from the Sponsor Medical Monitor or designee. Rosuvastatin therapy should be continued as assigned. Ezetimibe should be used in accordance with the FDA-approved package insert ([Appendix 7](#)). The subjects should also continue aldafermin/matched placebo through EOT as assigned.

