11.1 Definition and Grading Intensity of Adverse Events

An AE is defined as any untoward medical occurrence in a subject of clinical investigational participation administered a pharmaceutical product, whether or not considered drug related. A TEAE is an AE that is reported after a dose of study drug.

AEs include the following:

- Unfavorable changes in general condition
- Subjective or objective signs/symptoms
- Concomitant diseases or accidents
- Clinically relevant adverse changes in laboratory parameters observed in a subject in the course of a clinical study

AEs comprise all disturbances of general health status, subjective and objective disease symptoms (including laboratory abnormalities), and accidents observed in the context of a clinical trial, irrespective of a possible causal relationship with the administration of the trial substance. Events occurring in the framework of a clinical trial during drug-free and post-treatment periods or under placebo are also to be designated as AEs.

All AEs, regardless of how identified (e.g., volunteered, elicited, noted on physical examination), will be recorded throughout the study (i.e., from Screening until Follow-up).

Subjects will be followed for resolution of AEs, by querying the subjects for an ongoing AE until resolved or until any unresolved AEs are judged by the PI to have stabilized or if lost to follow-up. Resolution of all AEs will be promptly documented by the clinic on the subject's CRF.

Any pregnancy diagnosed during the study must be reported immediately to the PI and Sponsor, including pregnancy in female partners of male subjects. The pregnancy will be followed to term and/or outcome and this outcome must be reported to the Sponsor.

Pregnancy, in and of itself, is not regarded as an AE or SAE unless the birth results in a congenital anomaly/birth defect or there is suspicion that the study medication may have interfered with the effectiveness of a contraceptive medication or method.

The PI will rate the severity of AEs using the CTCAE v5 to grade the severity. Each CTCAE v5 term is a Medical Dictionary for Regulatory Activities (MedDRA) Lowest Level Term (LLT). The CTCAE displays Grades 1–5 with unique clinical descriptions of severity for each AE. Not all Grades are appropriate for all AEs. Therefore, some AEs are listed with fewer than five options for Grade selection. Grade 5 (Death) is not appropriate for some AEs and, therefore, is not an option.

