## 6.3 Clinical Laboratory Evaluations

Clinical laboratory evaluations include biochemistry, hematology and urinalysis. Actual values and change from baseline values of continuous laboratory tests will be summarized by treatment group for each visit. For categorical lab tests, frequency and percentage distribution will be presented by treatment group for each visit.

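### With six lipid and transaminase results blinded at every scheduled post-dose visit, AE tables will under-capture abnormalities in them, and no visible SAP table counts these from the laboratory data

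*Protocol*

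**What the plan says.** **Blinding.** Protocol section 9.1, Table 4, footnote g: "Lab results for ALT, AST, total cholesterol, LDL, HDL, and triglycerides are blinded to the site and sponsor from Week 2 onward". Each visit section from Week 2 to Week 30 repeats it, for example section 9.2.4: "Results for ALT, AST, Total Cholesterol, LDL, HDL, and triglycerides are blinded to the site and sponsor".

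**AE definition and grading.** Section 11.1 includes among AEs "Clinically relevant adverse changes in laboratory parameters observed in a subject in the course of a clinical study". It assigns grading to the investigator: "The PI will rate the severity of AEs using the CTCAE v5 to grade the severity". Section 6.1 defines the primary safety endpoint by the frequency, severity and timing of AEs and SAEs.

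**Prior signal.** Section 5.2.2 lists increased total cholesterol among the most common drug-related AEs in the earlier studies, seen mainly at higher doses.

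**Who sees LDL-C.** Section 9.4.14: "LDL-C samples will be analyzed and reported to the third-party Medical Monitor". That monitor is unblinded and sets the rosuvastatin dose. Active and placebo capsules look alike, and dosing decisions are hidden from the site.

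**SAP.** Section 6.2 builds its AE tables from reported treatment-emergent AEs. For laboratory data, section 6.3 says: "Actual values and change from baseline values of continuous laboratory tests will be summarized by treatment group for each visit". It gives frequencies only for categorical tests. Section 2.2 keeps unscheduled results in listings and out of all summaries.

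**The concern.** The person who must recognise and grade a laboratory AE does not see these six results at any scheduled visit after treatment starts. A low count of cholesterol or transaminase AEs would then partly reflect what the site could see. This matters most for lipids, where the protocol itself anticipates a drug effect and builds a rescue algorithm around it. If the SAP counted elevations from the laboratory data, the gap in AE reporting would do little harm. What is at stake is whether the report can say how many subjects in each arm had an elevation, and how severe it was.

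**Working it through.** There is no plan figure to reproduce. The check is a count, a reading of the passages side by side, and one illustration.

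1. **Reach of the blind.** Table 4 schedules post-dose chemistry at Weeks 2, 4, 8, 12, 18, 24, 25 and 30, which is 8 visits. Sections 9.2.4 to 9.2.11 state the blind at all of them: 8 of 8. Day 1 blood is drawn before dosing (section 9.2.3). The conditional lipid visit four weeks after Week 30 (section 9.2.12) is extra; it repeats no blinding statement but falls under footnote g.

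2. **Routes by which the site can still learn something.**
   - *LDL-C:* the third-party monitor contacts the site when LDL-C is above 100 mg/dL and more than 15 mg/dL above Day 1 on maximum tolerated rosuvastatin (9.4.14). Subjects uncontrolled on rosuvastatin plus ezetimibe are discontinued (9.4.14). Subjects above the same limits at Week 30 return for an additional visit, where AEs are recorded (9.1, 9.2.12). These routes show failure of treatment or persistence after it, not the first rise.
   - *ALT/AST:* section 8.3 iv requires repeat testing within 48 to 72 hours and possible discontinuation on multiples of baseline. It lets local results go to the site for subjects in remote areas. The visible text names no unblinded ALT/AST reviewer and no way for a blinded site to learn that a trigger was met.
   - *Total cholesterol, HDL, triglycerides:* no route is described.
   - Symptoms, and unblinded tests such as bilirubin, ALP, GGT and INR, remain visible.

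3. **What the SAP produces for these analytes.**
   - By-visit actual values and changes (6.3), with n, mean, SD, median, minimum and maximum (2.2).
   - Subject listings (2.2).
   - ANCOVA of each dose against placebo at Week 24 and other applicable visits (5.2, 5.3).
   - ALT/AST normalization responders (5.2, 5.3), which count values within the normal range, not rises, and have no lipid equivalent.
   - No visible shift table, threshold count, laboratory CTCAE grade or combined ALT/bilirubin count. Section 6.3 shows no visible redaction.

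4. **Why the existing summaries do not replace a count.**
   - Rosuvastatin is started and adjusted on LDL-C from Week 2 (9.4.14), so later LDL-C means reflect study drug plus rescue.
   - Subjects with uncontrolled LDL-C are withdrawn (9.4.14) and missing laboratory values are not imputed (SAP 2.2), so the worst cases leave the later means.
   - Repeat tests made at unscheduled visits enter no summary (SAP 2.2).
   - Illustration: take 38 subjects per arm (protocol Table 3) and the earlier mean ALT change of -35 IU at 3 mg (5.2.2). Assume a rise of 200 IU in k subjects and -35 IU in the rest. Arm mean = [200k - 35(38 - k)] / 38.
     - k = 1: (200 - 1,295)/38 = -28.8 IU
     - k = 2: (400 - 1,260)/38 = -22.6 IU
     - k = 3: (600 - 1,225)/38 = -16.4 IU

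   The mean still shows a fall in each case. The reported maximum would reveal the largest rise, but not whether one, two or three subjects had it.

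**The case against.** The strongest reply is that the effect will not be hidden. All six analytes are secondary endpoints, compared with placebo at each applicable visit with p-values and 90% confidence intervals. The maximum is tabulated and every value listed. Concomitant medication tables should show prescribed ezetimibe, and discontinuation reasons are tabulated. All of this stands. A dose-related shift in mean lipids would be visible, and an extreme value would show in the maximum. What these analyses lack is a by-arm count or grade of subjects with an on-treatment elevation.

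A reader might go further and infer that abnormalities in these analytes cannot be reported as AEs after dosing, that lipid or transaminase AEs will be near zero in every arm by design, or that a site hears of a lipid problem only when maximum rosuvastatin has failed. The documents do not support this: the discontinuation rule, the additional LDL-C visit, local results, symptoms and the unblinded liver tests are all further routes. A reader might also infer that nobody reviews ALT and AST during treatment. Section 8.3 iv presupposes that someone acts on them; the visible text simply does not say who or how.

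**Conclusion.** The point holds as under-capture, not as absence. The blind covers six analytes at 8 of 8 scheduled post-dose visits, and the visible SAP has no by-arm count or grade of elevations in any of them. The 8 of 8 measures results withheld, not AEs missed; the documents give no basis for estimating the latter. The gap is widest for total cholesterol, HDL and triglycerides, and partial for LDL-C. For ALT and AST it depends on how the blind and section 8.3 iv are reconciled. The ALT illustration rests on an assumed rise of 200 IU and shows only that a favourable mean can coexist with several large rises. The primary efficacy analysis, sample size and power are untouched. The change should be made before database lock.

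**What to change.** In SAP 6.3, add by-arm tables from the study laboratory data, produced after unblinding:

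- **(a)** Number and percent with LDL-C above 100 mg/dL and more than 15 mg/dL above Day 1, at Week 2 before study rosuvastatin and at any post-dose visit. This is a descriptive use of limits the protocol already states. The Week 2 initiation criteria are in Appendix 3, whose content is not shown, so the table should not be presented as applying them.
- **(b)** Number and percent exceeding the ALT/AST multiples of baseline in protocol section 8.3 iv, using that section's baseline (average of Day -42, Day -28 and Day 1) and not the SAP 2.2 baseline (last value before first dose).
- **(c)** Worst post-baseline CTCAE v5 grade for ALT, AST, cholesterol and triglycerides.

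Include unscheduled values in these tables as a stated exception to SAP 2.2; otherwise repeat tests drop out of the worst-value counts. Add a note to SAP 6.2 that the AE tables under-ascertain these analytes after Day 1 and must be read with the 6.3 tables. The primary safety endpoint stays as defined.

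Separately, the sponsor must reconcile the ALT/AST blind with the section 8.3 iv rules that depend on ALT/AST.

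The cost of the SAP change is some wording and a few extra tables from data already collected. The blind, visits and sample size do not change.

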iii. Adverse event of muscle symptoms (e.g., myalgia, pain, or weakness) or elevated creatine kinase:

A sample will be collected for assessment of CK within 48-72 hours, and CK assessment will be repeated if needed (refer to [Appendix 5](#)). At Weeks 12 and 24, the creatine kinase (CK) level will be compared to the subject's baseline level.

- If CK level is $\leq 3x$ baseline, subject will continue on aldafermin and over-encapsulated rosuvastatin.
- If CK level is $> 3x$ baseline, CK will be repeated within 48 - 72 hours and aldafermin and rosuvastatin will be held:
 - If CK is $\leq 3x$ baseline, subject can re-start on aldafermin and rosuvastatin based on the investigator's judgement.
 - If CK is $> 3x$ and $< 5x$ baseline, repeat CK levels within 48 - 72 hours while aldafermin and rosuvastatin on hold.
 - If CK is $\geq 5x$ baseline, aldafermin and rosuvastatin will be discontinued.

Upon repeat testing for subjects previously with CK $> 3x$ but $< 5x$ baseline:

- If CK is $\leq 3x$ baseline, subject can re-start on aldafermin and rosuvastatin based on the investigator's judgement.
- If CK level is $> 3x$ baseline, subject will discontinue aldafermin and rosuvastatin.

iv. Laboratory value(s) indicative of DILI:

- a) Elevation of AST or ALT $> 2x$ above subject-specific baseline value (calculated using the average of the Day -42, Day -28 and the Day 1 values) and total bilirubin $> 1.5 \times$ subject-specific baseline value, repeat testing of ALT, AST, and bilirubin must be performed within 48 - 72 hours. If there are persistent elevations (AST or ALT $> 2x$ baseline or TBL $> 1.5x$ baseline values) upon repeat testing, then close observation (testing and physical examination 2 - 3 times per week) should be implemented and discontinuation of aldafermin and rosuvastatin should be considered (see b [below](#)).
- b) A decision to discontinue or temporarily interrupt the study drug will be considered based on factors that include how much higher than baseline ALT and AST were relative to the upper limit of normal (ULN) and how much the on study ALT and AST levels have increased relative to baseline, in addition to whether there is concomitant elevation of bilirubin or INR. Aldafermin and rosuvastatin will be discontinued or temporarily interrupted as follows:
 - If baseline measurements (BLM) were $< 2x$ ULN, discontinue if ALT or AST increases to $> 5x$ BLM
 - If BLM $\geq 2x$ ULN but $< 5x$ ULN, discontinue if ALT or AST increases to $> 3x$ BLM

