- If BLM \geq 5x ULN, discontinue if ALT or AST increases to $> 2x$ BLM
- Discontinue if ALT or AST increase $> 2x$ BLM AND the increase is accompanied by a concomitant increase in TBL to $> 2x$ BLM OR the INR concomitantly increases by > 0.2
- In any subjects with signs and symptoms of fatigue, nausea, vomiting, right upper quadrant pain or tenderness, fever, rash, and/or eosinophilia ($> 5\%$).

- c) If the subject lives in a remote area, laboratory testing can be performed locally and the results should be promptly communicated to the investigator site.
- d) Close observation for suspected DILI will include:
 - Repeating liver enzyme and serum bilirubin tests two or three times weekly. Frequency of repeat testing can decrease to once a week or less if abnormalities stabilize or the study drug has been discontinued and the subject is asymptomatic.
 - Obtaining or re-confirming a detailed history of symptoms and prior or concurrent diseases.
 - Obtaining or re-confirming the history of concomitant drug use (including nonprescription medications and herbal and dietary supplement preparations), alcohol use, recreational drug use, and special diets.
 - Ruling out acute viral hepatitis types A, B, C, D, and E; autoimmune or alcoholic hepatitis; NASH hypoxic/ischemic hepatopathy; and biliary tract disease.
 - Obtaining a history of exposure to environmental chemical agents

Outside of situations listed above no aldafermin /matched placebo dose reductions will be allowed. Temporary drug holidays from aldafermin dosing ≤ 5 days will be allowed on a case by case basis for subjects for safety or tolerability but must be approved by the Sponsor Medical Monitor or designee. If drug is restarted and is still not tolerated, the subject should stop the medication as multiple drug holidays will not be allowed.

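### Protocol 8.3 iv: the liver-injury rules need ALT or AST values that are blinded to site and sponsor from Week 2, and no visible text names a reader for the scheduled results

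*Protocol*

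**What the plan says.** **Blinding.** Table 4, footnote g (Protocol 9.1): "Lab results for ALT, AST, total cholesterol, LDL, HDL, and triglycerides are blinded to the site and sponsor from Week 2 onward". The procedure sections for Weeks 2, 4, 8, 12, 18, 24, 25 and 30 (9.2.4 to 9.2.11) repeat it. Bilirubin, INR and CK are not on the blinded list.

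**Rules (Protocol 8.3 iv).** Under item a, AST or ALT above 2x baseline together with total bilirubin (TBL) above 1.5x baseline means that "repeat testing of ALT, AST, and bilirubin must be performed within 48 - 72 hours". If the elevation persists, close observation starts and "discontinuation of aldafermin and rosuvastatin should be considered". Item b rests the decision partly on "how much the on study ALT and AST levels have increased relative to baseline", then gives the action: "Aldafermin and rosuvastatin will be discontinued or temporarily interrupted as follows". Four numeric bullets follow, and then a fifth: "In any subjects with signs and symptoms of fatigue, nausea, vomiting, right upper quadrant pain or tenderness, fever, rash, and/or eosinophilia", where the only number is the eosinophil cut-off of 5%. For subjects in remote areas, item c says that "laboratory testing can be performed locally and the results should be promptly communicated to the investigator site". Close observation under item d includes "Repeating liver enzyme and serum bilirubin tests two or three times weekly".

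**Who sees blinded results.** Section 9.4.14 sends LDL-C to an unblinded third-party Medical Monitor, who assigns the rosuvastatin dose. Sections 8.3 ii and 11.3 add suspected statin-related events, reported to that monitor by the site. Section 11.4 sets up a cardiovascular adjudication committee. Section 10.5 lets the investigator obtain treatment assignment in an emergency. SAP Section 9 plans no interim analysis and names no monitoring committee in its visible text.

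**The concern.** The protocol gives stopping levels for liver enzymes and withholds those enzymes from the two parties who would normally apply them, the site and the sponsor. If nobody else is told to look, a subject whose ALT or AST crosses a stopping level at a scheduled visit may stay on both drugs because the crossing is never noticed. The repeat test and close observation do not cover this, since they begin only after someone has seen the first value.

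The blinding itself is sensible. The protocol does not give its reason, but Table 2 reports relative ALT changes at Week 12 of -43% and -44% on aldafermin, against 1% on placebo, so open enzyme results could reveal treatment. The gap is the missing reader.

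A second, smaller matter is the fifth bullet of item b. It places a list of common symptoms under a stop-or-interrupt instruction without an enzyme level or a severity grade, and does not say which of the two actions applies.

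**Working it through.** No power or alpha figure is involved. The check sets the provisions side by side and counts.

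**1. Does each numeric rule need ALT or AST?**

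| Rule in 8.3 iv | Condition | Needs ALT or AST? |
|---|---|---|
| a | ALT or AST > 2x baseline and TBL > 1.5x baseline | yes |
| b, bullet 1 | baseline < 2x ULN: ALT or AST > 5x baseline | yes |
| b, bullet 2 | baseline 2x to < 5x ULN: > 3x baseline | yes |
| b, bullet 3 | baseline at least 5x ULN: > 2x baseline | yes |
| b, bullet 4 | ALT or AST > 2x baseline, with TBL > 2x baseline or an INR rise > 0.2 | yes |

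That is 5 of 5. Sites can see bilirubin and INR, but neither starts any of these rules alone. Under item a, raised bilirubin can sustain the process at the repeat test, but entry still requires ALT or AST.

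**2. At which scheduled visits are the results blinded?** Weeks 2, 4, 8, 12, 18, 24, 25 and 30: 8 of 8.

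**3. Who is told to read them?** The named third-party review at those visits is LDL-C. At Week 30 it covers only subjects flagged at Week 25. ALT and AST are routed to a named reader at 0 of 8. The cardiovascular committee's review is itself blinded and concerns cardiac events, and Section 10.5 releases treatment assignment rather than laboratory values.

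**4. Where could a stop still change dosing?**
- Aldafermin: the last dose is taken at the Week 24 visit, so Weeks 2, 4, 8, 12 and 18, which is 5 visits.
- Rosuvastatin in statin-experienced subjects: it is dispensed again at Week 24 and continued to Week 30, and 8.3 iv stops rosuvastatin as well, so Weeks 24 and 25 also count.
- For at least one of the two drugs: 5 + 2 = 7 of the 8 visits.

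**5. How does the protocol treat similar cases?** Blinded LDL-C has a named reader, an algorithm and a route back to the site (9.4.14). Blinded on-treatment MRI has a stated exception for incidental findings (9.4.3). CK, used in 8.3 iii, is left unblinded. Scheduled ALT and AST have neither a reader nor an exception.

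**6. The fifth bullet.** It is 1 of 5 bullets in item b, and the only one with no enzyme level. Section 8.3 i, by contrast, acts at a related Grade 3 event or any Grade 4 event. Section 5.2.2 lists nausea among the most common drug-related events in healthy volunteers and in type 2 diabetes, mainly at higher doses. Section 5.1.1 says some NASH patients have fatigue, although most have no symptoms.

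**The case against.** **The assignment may exist elsewhere.** A Lab Manual is cited, parts of the text on the third-party monitor's system are blacked out, and the algorithms in Appendices 3 to 5 are not reproduced. A reader might infer that liver safety went unwatched in this trial. The documents do not support that; they show only that the visible text names no reader. The possibility stands and limits the conclusion, but a site working from 8.3 iv still needs to be told who acts.

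**Repeat tests look visible.** Items a, c and d order tests whose results must be seen to be useful. Item c can fairly be read as sending remote results to where other repeat results already go. The blinding text is attached to scheduled samples. It is therefore tempting, but not supported, to say that repeat tests are blinded too. The wording leaves that unclear. The supportable gap is first detection from scheduled samples.

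**The symptom bullet is meant jointly with an enzyme rise.** The title of trigger iv refers to laboratory values, and item b opens with ALT and AST. This largely stands: the bullet is a drafting fault, and one cannot conclude that the sponsor intended to stop drug for any nausea. Nor does it clash with the tolerability holiday of up to 5 days, which is a separate provision for situations outside the listed ones.

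**Rewording that bullet could do harm.** It is the only item b trigger that a blinded site can apply today. This stands, and it fixes the order of the changes.

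**Conclusion.** The concern holds for scheduled samples. As written, two provisions conflict: five numeric rules depend on ALT or AST, and those results are closed to site and sponsor at every scheduled post-baseline visit, with no visible assignment of a reader. The gap covers Weeks 2 to 18 for aldafermin, and extends to Weeks 24 and 25 for rosuvastatin in statin-experienced subjects. It should be closed because it concerns subject safety and costs little.

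Confidence is medium, since the conclusion assumes that no unseen manual, safety plan or blacked-out text already assigns the review. The documents give no rate of threshold crossings, so neither the number of subjects affected nor any effect on power or on the histology result can be claimed. The symptom bullet is a secondary wording fault.

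**What to change.** **First.** In 8.3 iv, assign the existing unblinded third-party Medical Monitor to review scheduled ALT and AST from Week 2 against the item a and item b thresholds, and to alert the site when one is met; other values stay blinded. State also that repeat tests ordered under 8.3 iv are either released to the investigator or reviewed by that monitor. If a safety plan, the Lab Manual or blacked-out text already does this, a cross-reference in 8.3 iv is enough.

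**Second, and only together with the first.** Reword the fifth bullet so that it applies when ALT or AST exceeds 2x baseline (or another level the sponsor sets) with any of the listed symptoms. Require a prompt liver test in symptomatic subjects, and say whether drug is stopped or interrupted.

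**Cost.** A small added task for a role that already exists, and a few lines of text. A symptomatic subject would stay on drug until the liver test is read, unless the investigator holds it.
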